## 6 DEFINITIONS FOR STATISTICAL ANALYSIS

The statistical analysis (interim analysis and final analysis) will be performed after completion of the following working steps:

- All relevant electronic case report form (eCRF) data is available and has been checked for errors and/or inconsistencies.
- All external subject data relevant for the analysis as described below, e.g.,
   eDiary data, laboratory data, is available and reconciled.
- All external non-subject data, e.g., grass pollen counts, is available.
- All queries relevant for the analysis have been answered and necessary editing
  of the database has been performed.
- Relevant data has been locked. The evaluation and classification of all intercurrent events and potential PDs have been completed and captured in the final BDRM minutes approved by the responsible persons.
- A detailed final SAP is available and approved by responsible personnel.

#### 6.1 Screen failures

For the purpose of summary tables and subject data listings, screen failures are defined as subjects who consent to participate in the clinical trial but are not subsequently randomised.

The number of screen failed subjects and the reason for screen failure will be tabulated.

## 6.2 Handling of withdrawals (drop-outs), missing values and outliers

Discontinued or withdrawn subjects will not be replaced if they withdrew due to AE. Subjects withdrawn early from the clinical trial due to other reasons may be replaced. Data collected for subjects whose participation is terminated is evaluated with all data as collected until withdrawal and during a possible follow-up for safety. Missing data for the primary variable on a by-day level will be handled using multiple imputation methods. Similarly, missing data in covariates included in the analysis model of CSMS will be imputed to allow the inclusion of all subjects from the FAS into the primary analysis.

ncomplete dates will be imputed temporarily for the categorisation of AEs or concomitant medications. The corresponding strategies are described in the corresponding sections.

## 6.3 Visit definition for analysis

All scheduled visits will be analysed as defined in the clinical trial protocol and the numbering is taken from the eCRF.

## 6.4 Baseline and screening

A baseline measurement will be defined as the latest measurement obtained prior to the first administered dose of investigational drug/placebo.

Screening is defined as the period before Visit 2. In case several measurements are taken during the screening period, only the later one is used for analysis.

## 6.5 Reference day for the statistical analysis

Day 1 is defined as the date of first administration of investigational drug/placebo. Relative days for statistical analysis will be calculated relative to Day 1. There is no Day 0 (the day before the first administration of investigational drug/placebo is day - 1).

#### 6.7 Definition of Grass Pollen Season

For the purpose of statistical analysis, the start and end of the entire grass pollen seasons (GPS) and the peak pollen seasons of each year (if applicable) will be determined based on the daily pollen counts from pollen traps local to the trial sites. The final decisions regarding the site-specific (peak) pollen periods to be applied for the eDiary related endpoints will be determined prior to unblinding of the database and documented in the BDRM minutes for each year.

## 7 STATISTICAL ANALYSIS SPECIFICATION

## 7.1 Specifications related to whole analysis

## **7.1.1 Tables**

Data will be summarised using suitable descriptive statistics depending on the structure of the data. Summary tables will be grouped by treatment group and by visit.

If not specified otherwise, the following treatment groups will be included:

- PQ Grass, and
- · Placebo.

For continuous data, the basic statistics include the number of subjects with data available, arithmetic mean, SD, median, first and third quartile, minimum, maximum. Two-sided 95% CIs will be presented for the arithmetic mean based on the normal approximation, whenever appropriate.

In general, the minimum and maximum will have the same number of decimals as collected. Mean, median the quartiles and the CI for the arithmetic mean will be

displayed one additional decimal and the SD will be displayed with two additional decimals. For summary statistics, calculated averages will be displayed as if they were collected with one digit.

Categorical data will be displayed in frequency tables showing the number and percentage of subjects for each outcome category. Percentages will be displayed with one decimal.

## 7.1.2 Data listings

Individual data will be listed. All relevant generated and transformed variables will be listed next to the original data items as well. Calculated averages will be listed with 3 digits.

If not mentioned differently, data listings will be based on randomised subjects only, only a reduced set of listings will be generated for screen failures.

In general, listings will be sorted by subject number. Each listing will contain the subject number and randomised treatment group. The clinical trial period will be additionally displayed whenever applicable and reasonable.

Subject data listings for event-based data (e.g., AEs or concomitant medications) will be sorted by subject number, by event start date and then alphabetically by reported term and coded term.

## 7.2 Disposition of subjects

#### Clinical trial duration

The clinical trial duration until Visit 11 in days is defined as last subject last visit (until Visit 11) – first subject first visit + 1.

The clinical trial duration including safety follow-up in days is defined as last subject last

follow-up call – first subject first visit + 1.

The clinical trial duration until Visit 11 and the clinical trial duration including safety followup will be displayed overall, including all subjects (i.e., treated subjects as well as screen failures). Separate summaries will be generated for Year 1, Year 2 and combined, if applicable.

# Subjects screened, randomised, treated, completed and discontinued prematurely

Subjects are defined as completing the clinical trial, including the safety follow-up, if the item "Premature study termination" is ticked as "No" on the "End of study evaluation" page.

Subjects are defined as prematurely discontinuing the clinical trial if this item is marked as "Yes".

Subjects are defined as completing treatment, if the item "Premature treatment termination" is ticked as "No" on the "End of treatment" page. Subjects are defined as prematurely discontinuing treatment if this item is marked as "Yes".

A summary table will be created including:

- the number of screenings (including re-screenings),
- the number of subjects who were screened (i.e., signed the informed consent),
- the number of screen failures,
- the number of subjects who were randomised,
- the number of subjects who were treated,
- the number and percentage of subjects who completed treatment,
- the number and percentage of subjects who prematurely discontinued treatment,
- the number and percentage of subjects who completed the clinical trial including safety follow-up, and
- the number and percentage of subjects who prematurely discontinued the clinical trial.

This analysis will be repeated by for Europe and United States separately, by pooled geographical region (if applicable), and geographical region used for randomisation.

#### Reason for discontinuation of treatment or clinical trial

The number and percentage of subjects discontinuing treatment including the primary reason for end of treatment and the number and percentage of subjects discontinuing the clinical trial including the primary reason for end of trial will be summarised by treatment group and overall for the FAS.

## **Analysis Sets**

A summary table will be created showing the number of subjects randomised and the number and percentage of subjects included in each of the defined analysis sets (FAS and SAF), according to randomised treatment group and overall. Percentages will be calculated based on the randomised subjects.

#### Subjects per visit

The number and percentage of subjects participating at each (scheduled) visit will be provided by treatment group and overall for the FAS.

In addition, the number and percentage of subjects having the 12- and 24-weeks safety follow-up documented will be provided by treatment group and overall for the FAS.

## 7.3 Demographics and baseline characteristics

Demographic information collected at screening (Visit 1) will include age (at date of informed consent), sex, race, ethnicity, childbearing potential (for female subjects) and methods of contraception (if applicable), as well as smoking and alcohol consumption habits.

Height at screening (latest measurement from Visit 1 and Visit 1a, if applicable) will be displayed in cm and weight at screening (latest measurement from Visit 1 and Visit 1a, if applicable) in Kilograms (kg). Body Mass Index (BMI) will be calculated as

weight[

 $height[m]_2$ 

and displayed in kg/m^2.

Demographic data will be summarised by treatment group and overall for the FAS, and listed by subject. Separate summaries will be generated for Year 1, Year 2 and combined, if applicable.

## 7.4 Medical History and Concurrent Diseases

#### 7.4.1 Definitions and conventions

A medical and allergy history including details regarding all illnesses, asthma (past or current), surgeries and any kind of allergies (to assess eligibility) at screening must be recorded in the eCRF. A full history for the 5 years prior to screening and any other significant medical history is to be documented.

Concurrent diseases and medical history will be coded using the MedDRA dictionary (Medical Dictionary for Regulatory Activities) according to the version and update strategy as defined in the coding guideline for this clinical trial.

A concurrent disease is defined as any disease, for which either no stop date was documented (i.e., disease is ongoing) or the stop date is later than the date of Visit 1. All other diseases are defined as medical history. Incomplete stop dates will be estimated using the first possible date in order to define whether a disease is concurrent, i.e., it will be assumed that a disease is not ongoing at trial start whenever the end date indicated that the disease ended in the same month or year as Visit 1 occurred.

In detail, the following assumptions are made for the determination whether a disease is considered as medical history or concurrent disease:

- If the end date is incomplete, year and month are available and the day is missing, it is assumed that the disease ended at the first day of the corresponding month.
- If the end date is incomplete, year is available and month and day are missing, it is assumed that the end date is the 01-Jan of the corresponding year.
- If the end date is completely missing it will be assumed that the disease is still ongoing at Visit 1 and thus the entry is considered as concurrent disease. The only exception are cases with completely missing end date that are explicitly ticked as being "not ongoing at Visit 1" in the eCRF and the end date is unknown.

The duration of grass pollen allergy history until trial start will be calculated as: month of first injection of investigational drug/placebo – start month of first expression of grass pollen allergy that was entered in the grass pollen history section of the eCRF.

In case the month is missing, it is assumed that the allergy started in January of the corresponding year. Entries without a year will not be considered for this calculation.

The duration of grass pollen allergy history in months will be summarised by treatment group for the FAS.

## 7.4.2 Medical history and concurrent diseases (non-allergy related)

Concurrent diseases and medical history not related to any allergy will be summarised by treatment group. In this summary table, the diagnoses and indications will be presented by MedDRA preferred term (PT) and grouped under the respective system organ class (SOC). The SOCs and the PTs within SOCs will be sorted by decreasing frequency in the total column.

Separate tables will be created for non-allergy related medical history and concurrent diseases for the FAS.

Non-allergy related concurrent diseases and medical history will be listed by subject.

## 7.4.3 Grass pollen allergy history and status at start of trial

Symptoms related to grass pollen allergy (i.e., allergic conjunctivitis, allergic rhinitis, allergic cough, allergic asthma and allergic urticaria) will be summarised separately by whether these symptoms were ongoing at trial start (i.e., occurred during at least 2 GPSs before screening) or not.

Number and percentage of subjects with the corresponding symptoms related to grass pollen allergy will be presented by treatment group, differentiating further by severity and whether allergic treatment was taken (i.e., taken any medication for allergy in the last two GPSs prior to screening).

All grass pollen allergy history related information including start and end dates of symptoms related to grass pollen allergy will be listed by subject.

Grass pollen related concurrent diseases and medical history will be summarised for the

FAS. Separate summaries will be generated for Year 1, Year 2 and combined, if applicable.

## 7.4.4 Other allergy history

Concurrent other allergies (ongoing at trial start) will be summarised by treatment group and reported term (including "Other" as collected in the eCRF), differentiating further by severity and whether allergic treatment was taken for the FAS.

All other allergy history (past or present) will be listed by subject.

#### 7.4.5 Asthma status

The baseline asthma status is either "present (past and/or current)" for all subject with documented past and/or current asthma or "not present" for all subject without any documented asthma (no documented medical history also means no asthma). Frequency tables with be provided for the FAS displaying the number and percentage of subjects with present or not present asthma and the variable will be used for subgroup analysis.

# 7.5 Prior and concomitant medications, procedures and non-drug medical interventions

All prescription and over the counter medications for relief of allergy symptoms taken over the last 2 years and those used for other conditions in the last 1 month before screening should be recorded in the eCRF. Details of any concomitant medication used during the clinical trial including all prescription and over the counter medications taken by the subject during the clinical trial until end of study (EoS) must be documented in the eCRF at each visit (scheduled or unscheduled).

All prior and concomitant medications documented in the eCRF will be coded using the World Health Organisation (WHO) Drug dictionary according to the version and the update strategy as defined in the coding guideline for this clinical trial.

All prior and concomitant procedures and non-drug medication interventions documented in the eCRF will be coded using the medical dictionary of regulatory activities (MedDRA) according to the version and update strategy as defined in the coding guideline for this clinical trial.

Prior medications are defined as medications that started prior to first injection of investigational drug/placebo. In case the start date is missing or incomplete with the possibility that the medication was taken prior first injection of investigational drug/placebo, it will be assumed that at least one dose was taken prior to the first injection of investigational drug/placebo and thus the entry will be considered as prior medication.

Concomitant medications are defined as any medication with at least one dose taken at or after the first injection of investigational drug/placebo, i.e., for all end dates larger or equal to first documented injection of investigational drug/placebo. In case the end date is missing or incomplete with the possibility that the medication was taken after the first injection of investigational drug/placebo, it will be assumed that at least one dose was taken after the first injection of investigational drug/placebo and thus the entry will be considered as concomitant medication.

Prior and concomitant medications will be summarised separately by display of the absolute and relative frequency by treatment group using as denominator the number of subjects in the respective treatment group and overall in the FAS. In these summary tables, medication will be classified according to WHODD ATC2 (Anatomical Therapeutic Chemical Classification) name and base substance.

Prior and concomitant procedures and non-drug medical interventions will be summarised by primary SOC and PT in the FAS by treatment group and overall.

The summary tables will be sorted by decreasing frequency in the total column within levels.

#### 7.6 Other baseline characteristics

Other baseline characteristics are defined as the results of assessments that are assessed at screening and/or baseline only. Assessments that are performed at several visits including screening and/or baseline are presented in the corresponding sections (efficacy, safety or exploratory). Other baseline

characteristics are the results of Skin Prick Test (SPT), the results of spirometry, and immunoglobulins collected at screening for eligibility (ImmunoCAP). These data will be summarised by treatment group and overall for the FAS, and listed by subject.

#### 7.6.1 Skin Prick Test

A SPT using various allergens will be performed at screening to assess eligibility of subjects. A standard negative control will be used and histamine control solution (1.0%) will be used for the positive control.

The reaction grade (negative, positive) will be displayed in a frequency table further differentiated by case history of symptoms.

## 7.6.2 Spirometry

Spirometry will be performed at screening (Visit 1) and Visit 1a (if applicable) for all subjects

to determine eligibility. At screening, the FEV₁ should be ≥70% of predicted with a FEV₁/FVC ratio >75%.

Summary statistics will be created for spirometry measurements at screening by treatment group for the FAS.

## 7.6.3 Immunoglobulins at screening

Blood samples will be collected at screening for evaluation of eligibility:

- Serum total IgE [U/mL]
- Serum grass-specific IgE [kUA/L]
- Serum grass-specific IgG4 [mg/L]

Results will be summarised by display of the absolute and relative frequencies per class by treatment group for the FAS.

## 7.7 Efficacy

## 7.7.1 Primary efficacy analyses

The primary efficacy variable is the daily Combined Symptom and Medication Score (CSMS) averaged over the peak grass pollen season (GPS).

#### 7.7.1.1. Primary estimand for primary efficacy analysis

In alignment with the addendum to International Council for Harmonisation of Technical Requirements for Pharmaceuticals for Human Use (ICH) E9, the estimand for the primary efficacy analysis in this clinical trial is defined by the following attributes (see Section 9.3.5.1 of the clinical trial protocol):

## **Table 8 Primary estimand**

Treatment	"PQ Grass" (PQ Grass 27600 SU) versus "Placebo".

Population	Subjects with seasonal allergic rhinitis and/or rhinoconjunctivitis induced by grass pollen exposure, as defined by the inclusion and exclusion criteria of the clinical trial, who received at least 1 injection of the clinical trial medication  PQ Grass or placebo.  The analysis will be based on the FAS.
Variable	CSMS averaged over the peak GPS for each subject.  The daily CSMS is calculated as the sum of the dSS and the dMS data recorded in the eDiary.  The average CSMS over the peak GPS will be calculated as sum of the daily CSMS within the peak GPS divided by the number of days of the peak GPS where the CSMS has been collected.
Population level summary	Difference in mean CSMS between the PQ Grass and placebo group.

## 7.7.1.2. Daily Combined Symptom and Medication Score

The daily CSMS is the sum of the daily Symptom Score (dSS) component of the CSMS and the daily Medication Score (dMS) component of the CSMS calculated from the data recorded in the eDiary.

The dSS is calculated as the sum of the severity of conjunctival symptoms (2 items) and nasal symptoms (4 items) divided by 6 for each subject and day (see Table 9).

The severity of symptoms is recorded on a 4-point severity scale:

- 0 = No symptoms,
- 1 = Mild symptoms
   (sign/symptom clearly present, but with minimal awareness and easily tolerated),
- 2 = Moderate symptoms
   (definite awareness of sign/symptom that is bothersome but tolerable), and
- 3 = Severe symptoms
   (sign/symptom that is hard to tolerate; causes interference with activities of
   daily living and/or sleeping).

Table 9: Conjunctival and nasal symptoms of the CSMS

Conjunctival Symptoms	Itchy/red eyes *
	Watery eyes
N 10 1	Blocked nose
Nasal Symptoms	Runny nose

Itchy nose
Sneezing

\* Maximum of single items "Itchy eyes" and "Red eyes" is used for analysis.

The dMS is equal to the raw score assigned to each subject and day for the medication with the highest step taken that day.

Thereby, medication is rated on a 4-point scale:

- 0 = No relief medication used,
- 1 = Oral antihistamine/Ocular antihistamine (Step 1 medication),
- 2 = Intranasal corticosteroids (Step 2 medication) with Step 1 medication(s), and • 3 = Oral corticosteroids (Step 3 medication) with Step 1 and Step 2 medications.

A subject will be assigned 1 score (i.e., 1, 2 or 3) per day based on at least 1 dose of the medication of the highest step taken that day, regardless of if more than 1 medication from different steps has been taken. In case, no relief medication is taken, a score of 0 is assigned. For example, a subject taking antihistamine eye drops (Step 1), an antihistamine tablet (Step 1) and intranasal corticosteroids (Step 2) on the same day would be allotted a score of 2 for the Step 2 medication taken.

## 7.7.1.4. Average CSMS over the peak GPS

The average CSMS over the peak GPS is calculated as the sum of the daily CSMS within the peak GPS divided by the number of days of the peak GPS where the CSMS has been collected or imputed.

For the primary analysis, all subjects in the FAS will be included. This will be done by using multiple imputation methods on a by-day level. The average CSMS over the peak GPS can then be calculated based on all days within the peak GPS per imputation.

An analysis providing summary statistics based on observed cases will also be performed

Summary statistics will be provided for the average CSMS over the peak GPS by treatment group based on observed cases.

#### 7.7.1.5. Statistical analysis method

The primary efficacy analysis for this clinical trial will be a comparison of the mean average CSMS during the peak GPS in the PQ Grass versus the placebo group.

The following null and alternative hypotheses will be tested for the primary endpoint, based on all subjects who received at least 1 injection of the clinical trial medication, i.e., are included in the FAS (two-sided test):

μ: arithmetic mean of the average CSMS over the peak GPS

The primary efficacy endpoint will be evaluated using a linear mixed model.

The difference between PQ Grass and placebo will be estimated using least squares (LS) means. Two-sided 95% repeated confidence intervals (RCIs) for the difference between treatment groups will be provided at the interim and (if applicable) at the final analysis, which will ensure 95% probability despite calculation at the interim and (if applicable) final analysis.

The difference between treatment groups will also be presented in percent relative to the LS mean in the placebo group, and the CI will be calculated by approximating the SE using the delta method.

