#### Statistical methods

This is the pivotal Phase III study with PQ Grass. The primary endpoint of the study will be the CSMS averaged over the peak GPS.

The difference in CSMS between PQ Grass and placebo will be evaluated using a linear mixed model. Subjects with missing daily CSMS during the peak GPS will be included in the primary analysis by using multiple imputation methods to impute missing values on a by-day level.

The statistical analysis will be performed using a linear mixed model. In the context of the adaptive design, a 1-sided testing will be used using group sequential Pocock boundaries chosen such that an overall 1 sided type 1 error rate of 2.5% was preserved.

For the interim analysis after Year 1, the 1-sided p-value was therefore to be compared with  $\alpha$  = 0.01419 for a statistically significant superiority of the active treatment over placebo.

The difference between PQ Grass and placebo will be estimated using least squares (LS) means. Two-sided appropriate confidence intervals (CIs) for the difference between treatment groups

[figure not shown]

will be provided. The difference between treatment groups will also be presented in percent relative to the LS mean in the placebo group.

The secondary endpoints will generally be analyzed using a similar statistical approach as the primary endpoint. The statistical hypotheses for the key secondary endpoints will only to be tested in a confirmatory sense if the analysis of the primary endpoint is statistically significant. Multiplicity in the key secondary endpoints will be addressed.

The frequency, relationship and severity of AEs and frequency of premature discontinuations from treatment or study due to AEs will be assessed within each treatment group.

**Adjudication Committee:** Yes **Trial Oversight Committee:** Yes

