## 3 GENERAL

This statistical analysis plan

follows the principles of the Guidelines ICH Topic E3, ICH Topic E9, and ICH Topic E9(R1). It gives all details for the interim and final statistical analysis of this clinical trial.

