## 3.1 Analyses planned and already performed

One interim analysis will be conducted after the grass pollen season (GPS) of the first year (Year 1) is terminated and all subjects treated in Year 1 have completed Period 3 (PreGPS, Onset of GPS, During GPS and End of GPS assessments, including Visit 11).

Based on the results of the interim analysis one of the following 3 scenarios will occur:

- The trial stops for success.
- The trial progresses to Year 2.
- The trial stops for futility.

In case the trial progresses to Year 2 based on the interim result, a recalculation of the sample size will be performed, and the sample size may be adapted.

In case the trial is terminated based on interim analysis results and this decision is documented in writing, the results of the primary analysis will be shared with the Sponsor. Furthermore, group unblinded topline results of efficacy will be prepared and distributed to the Sponsor. As the subjects will continue with the safety follow-up, all personnel involved in the conduct of the trial will stay blinded until the database including safety data has been locked.

In case the trial will continue into Year 2, no unblinding of personnel involved in the conduct of the trial will occur after the interim analysis. After all subjects enrolled in Year 2 have completed Period 3 (including Visit 11), all data relevant for the efficacy analysis will be locked and group unblinded topline results of efficacy will be generated and distributed to the Sponsor. All personnel involved in the conduct of the trial will stay blinded until the last safety follow-up is performed and all data.

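### Do the protocol's one-sided test at 0.01419 and the SAP's two-sided primary test lead to different Year 1 decisions?

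*SAP*

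**What the plan says.** Protocol, Statistical methods: "In the context of the adaptive design, a 1-sided testing will be used using group sequential Pocock boundaries", chosen so that "an overall 1 sided type 1 error rate of 2.5% was preserved". For Year 1, "the 1-sided p-value was therefore to be compared with" a level of "0.01419 for a statistically significant superiority of the active treatment over placebo".

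SAP 7.7.1.5 gives the primary hypotheses for subjects who "are included in the FAS (two-sided test"). It then calls for "Two-sided 95% repeated confidence intervals (RCIs) for the difference between treatment groups" at the interim and, if there is one, at the final analysis, with 95% coverage kept over both looks. The public text of 7.7.1.5 and 7.7.1.6 prints no critical level for either look.

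SAP section 3 says of the document: "It gives all details for the interim and final statistical analysis of this clinical trial". SAP 3.1 says that if the trial goes on to Year 2, "a recalculation of the sample size will be performed, and the sample size may be adapted".

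**The concern.** The two documents label the same pivotal test differently and give no conversion. The only printed threshold, 0.01419, belongs to a one-sided p-value, while the SAP's test yields a two-sided one. The matching two-sided value, 0.02838, appears nowhere. An analyst working from the SAP alone might compare a two-sided p with 0.01419, which roughly halves the error rate and costs power. Or the analyst might use an unadjusted 0.05 at each look, which inflates the error rate. The choice would decide whether the trial stops for success, and it would open or close the gate to all key secondary tests.

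A second worry concerns Year 2. The sample size may be changed after an unblinded look, yet the visible text names only a linear mixed model and Pocock boundaries. Pooling both years against an unchanged boundary after a data-driven change of size does not in general guarantee 2.5%.

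**Working it through.** **Inputs.** From the protocol: overall one-sided error 2.5%, interim one-sided level 0.01419, 555 subjects at the interim, 1:1 allocation, two looks. From SAP 7.7.1.5: a two-sided test and a two-sided 95% repeated interval. The documents do not give the information fraction *t* at the interim, so it is an assumption and is varied.

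**1. The plan's own figure.** A two-look Pocock constant *c* solves 1 − P(Z₁ < c, Z₂ < c) = 0.025, with corr(Z₁, Z₂) = √t.

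| t | one-sided level |
|---|---|
| 0.35 | 0.01390 |
| 0.40 | 0.01414 |
| 0.409 | 0.01419 |
| 0.45 | 0.01440 |
| 0.50 | 0.01469 |

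So 0.01419 is a proper Pocock level if t is about 0.41, which would mean a planned total near 555 / 0.4094 ≈ 1,356. It is not the equal-spacing value. Without *t* in the documents it is consistent with Pocock but cannot be confirmed.

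**2. One-sided against two-sided.**
- One-sided 0.01419 gives z = Φ⁻¹(1 − 0.01419) = 2.192.
- The two-sided equivalent is 2 × 0.01419 = 0.02838, with |z| = 2.192.
- Solving the two-sided 5% Pocock problem separately at t = 0.409 gives 0.02838 and |z| = 2.192 again.
- A repeated interval on that boundary is the estimate ± 2.192 SE, a nominal level of 1 − 0.02838 = 97.16% at the interim. It excludes zero in favour of PQ Grass exactly when the one-sided p is below 0.01419.
- With 555 subjects at 1:1, the smallest significant difference is 2.192 × √(4/555) = 0.186 SD under either label.

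**3. What a wrong pairing would do.**
- *Two-sided p against 0.01419 at both looks.* The one-sided level is 0.01419 / 2 = 0.007095, z = 2.452. Overall one-sided error is 1.28% at t = 0.40. Where interim power should be 90%, the drift is 2.192 + 1.282 = 3.474 and power becomes Φ(3.474 − 2.452) = 84.6%. Where it should be 80%, the drift is 2.192 + 0.842 = 3.034 and power becomes Φ(3.034 − 2.452) = 71.9%.
- *Unadjusted two-sided 0.05 at both looks (z = 1.960).* Overall one-sided error is 4.3% at t = 0.40 and 4.2% at t = 0.50.
- *Unadjusted 0.05 at the interim only.* Overall one-sided error is 3.44% at t = 0.409.

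Neither pairing is in the documents. The protocol ties 0.01419 to the one-sided p-value in the same sentence. The SAP gives no 5% test level for the primary endpoint. Its 5.0% two-sided alpha, in 7.7.2, is for the key secondary endpoints. Its primary interval is adjusted for two looks, which rules out an unadjusted 0.05 at each.

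**4. Final test after recalculation.** Suppose both years were pooled against c = 2.192. With second-stage information n₂ on a scale where the planned total is 1, the chance of rejecting under the null given Z₁ = z₁ is 1 − Φ[(c√(t + n₂) − z₁√t) / √n₂]. Taking the worst n₂ for every z₁ and integrating over z₁ < c, for t of 0.40 to 0.50, gives these upper bounds on the one-sided error:
- second stage raised up to twofold: about 2.7%
- up to fourfold: about 2.9%
- unlimited increase: about 3.5%
- increase or decrease without limit: about 3.7%

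These are maxima over every possible rule. Under a common rule, which raises the second stage twofold or fourfold only when conditional power is at least 50%, naive pooling gives 2.2% to 2.4% (t from 0.38 to 0.50). That is below 2.5%.

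**The case for a change.** The strongest case for acting is that the SAP claims to be complete on the interim analysis, yet a reader of it alone cannot find the number that stops the trial. The conversion to 0.02838 and the link between the repeated interval and the Pocock boundary have to be inferred. The final-stage method is not stated at all, although the sample size may change on unblinded data. A few sentences would settle all of this before unblinding.

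Part of this stands. The labels do differ, and the documents do not name the boundary behind the repeated interval. The inference is short, however: Pocock is the only boundary either document gives, and doubling a one-sided level is routine for any statistician programming the interim.

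The complaint of silence is weaker, because the public SAP is visibly incomplete at this point. In 7.7.1.5 the hypotheses are announced but the formulae are absent. Section 7.7.1.3 does not appear. Section 7.7.1.6, on the adaptive design, is two sentences long, with no futility or recalculation rule, although 3.1 relies on both. SAP 7.7.1.1 cites a protocol section, 9.3.5.1, that is not in the public protocol. The reference list holds a textbook on group sequential and confirmatory adaptive designs that no visible text cites. So the absence of a boundary or of a combination method can be asserted only for the public text. Equally, that text does not show that a valid final-stage method is in place; it specifies neither such a method nor naive pooling.

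**Conclusion.** The Year 1 decision does not depend on which document is followed. One-sided 0.01419 and two-sided 0.02838 in favour of PQ Grass are one rule, z = 2.192 or 0.186 SD with 555 subjects, and the repeated interval fits it. This rests on building that interval on the Pocock boundary, the only one given. The difference in sidedness is a slip of labelling.

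The error rates of 1.3% and 4.3% measure misuse that the texts argue against. The 2.7% to 3.7% figures are worst cases of a pooled test that no document prescribes, and an ordinary enlargement rule stays below 2.5%. Whether the final test uses a combination method cannot be judged from the cut section. That is a limit of the public text, not a demonstrated fault. These figures also rest on assumed values of *t*, though they move little with it. The gap is missing detail that the trial statisticians would fill in the obvious way, and no change to the plan follows.
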